9.4.11 EXPLORATORY ANALYSES

Additional exploratory endpoints will be collected. These include cuff closure time (the time required to close the vaginal cuff as measured from time of conclusion of uterine excision to time of placement of the final Zip-stitch[™] clip or completion of final suture), total surgical time (calculated based on procedure start and end times (time from first incision to final port closure)), and whether implant material can be observed in the vaginal canal during visual cuff inspection.

Cuff closure time and total surgical time will be summarized by providing the number of subjects with available data (n), the mean, median, standard deviation, minimum, and maximum values. Observation of implant material will be reported and compared between test and reference groups.

10 SUPPORTING DOCUMENTATION AND OPERATIONAL CONSIDERATIONS

10.1 REGULATORY, ETHICAL, AND STUDY OVERSIGHT CONSIDERATIONS

10.1.1 INFORMED CONSENT PROCESS

CONSENT/ASSENT AND OTHER INFORMATIONAL DOCUMENTS PROVIDED TO PARTICIPANTS

Consent forms describing in full relevant detail the Zip-stitch[™] study procedures and components, as well as risks, are given to the subjects. This Informed Consent Form will be approved by an IRB prior to enrollment.

Written documentation of informed consent is required prior to enrollment.

CONSENT PROCEDURES AND DOCUMENTATION

Informed consent is a process initiated prior to an individual's agreeing to participate in this study and continues throughout the individual's study participation. Extensive discussion of risks and possible benefits of participation will be provided to the subjects and their families. Consent forms will be IRBapproved, and the subject will be asked to read and review the document. The investigator will explain the research study to the subject and answer any questions that may arise. All subjects will receive a verbal explanation in terms suited to their comprehension of the purposes, procedures, and potential risks of the study and of their rights as research subjects. Subjects will have the opportunity to carefully review the written consent form and ask questions prior to signing. Subjects should have the opportunity to discuss the study with their surrogates or think about it prior to agreeing to participate. Study participation will be discussed in a manner which will avoid any potential or perceived coercive influence by the patient's surgeon. Should subjects elect to participate they will sign the informed consent document prior to any procedures being done specifically for the study. The subjects may withdraw consent at any time throughout the course of the study. A copy of the informed consent document will be given to the subjects for their records. The rights and welfare of the subjects will be protected by emphasizing to them that the quality of their medical care will not be adversely affected if they decline to participate in this study.

10.1.2 STUDY DISCONTINUATION AND CLOSURE

This study may be temporarily suspended or prematurely terminated if there is sufficient cause. Written notification, documenting the reason for study suspension or termination, will be provided by the

suspending or terminating party to the principal investigator, the sponsor: ZSX Medical LLC, and regulatory authorities including appropriate IRBs and FDA.

Circumstances that may warrant termination or suspension include, but are not limited to:

- Determination of unexpected, significant, or unacceptable risk to participants
- Insufficient compliance to protocol requirements
- Data that are not sufficiently complete and/or evaluable
- Determination of futility

Study may resume once the concern leading to study suspension is addressed sufficiently to satisfy the sponsor, IRBs and FDA.

The primary study stopping rule is defined in terms of subject safety. The study will be paused and an unblinded analysis will be performed by the independent safety monitor if at least three cuff dehiscences and a failure rate of at least 5% of the enrolled study population has been realized. Upon unblinded review, the study will continue unless vaginal cuff closure failures with study test device (Zipstitch™ clips) are found to be at least 3 cases and a rate of greater than 5% of the enrolled study population. Study stoppage rules apply only to the test device and not to the standard-of-care reference device (VICRYL™).

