3.1 PRIMARY ENDPOINT

(Efficacy) Frequency of Implant Passing Events

Frequency of implant passing events will be reported for all subjects. Failure in this endpoint is defined, on a per patient basis, as the presence of one or more spontaneous implant passing events. A single event may be one or more clips or sutures being spontaneously passed by the patient (*i.e.*, not removed by medical staff).

Frequency of implant passing (either clips or sutures) will be explicitly collected at each follow-up visit; however, events may be reported between visits or during unexpected visits. When implant passing is reported, subjects will be asked to collect and provide passed implants, and an in-person evaluation will be performed. This will involve a visual cuff closure and healing assessment.

In the final analysis of this primary efficacy analysis, the rate of implant passage will be reported through six weeks. The primary objective of this endpoint is to observe a study population failure rate of less than 5% and is neither statistically-driven nor comparative.

(Safety) Frequency of Vaginal Cuff Dehiscence

Vaginal cuff dehiscence is defined as rupture of the surgical wound requiring surgical re-intervention. The proportion of subjects who experience vaginal cuff dehiscence up to six weeks after surgery will be evaluated. In the final analysis of this primary safety endpoint, failure will be reported, and test and control groups will be compared using Fisher's exact test to assess for a possible difference between groups.

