3.2 SECONDARY ENDPOINTS

(1) Binary assessment of cuff closure

Cuff closure will be assessed by an independent surgeon at one and six weeks, as well as at six months. Surgeon visual assessment will grade vaginal cuffs as closed or not closed, or the surgeon may indicate that it was not possible to determine. As such, subjects who experience a dehiscence and are considered a failure in analysis of the primary study safety endpoint will be a failure in this secondary endpoint (lack of closed cuff at six weeks). However, subjects could fail this secondary endpoint without failing the primary study safety endpoint.

In cases in which a surgeon is unable to assess cuff closure, the most recent successful evaluation of cuff closure (including intra-operative evaluation) will be used; reason for inability to determine will be recorded. Fisher's Exact Test will be used to assess possible significance of a difference in cuff closure scores between test and reference groups.

(2) Binary assessment of cuff healing

Vaginal cuff healing will be visually assessed by an independent surgeon at six weeks and six months. Surgeon visual assessment will grade vaginal cuffs as healed or not healed, or the surgeon may indicate that it was not possible to determine. In cases in which a surgeon is unable to assess cuff healing, the most recent successful evaluation of cuff closure will be used. If no prior evaluation has established cuff healing, the cuff will be assumed to have not healed yet. Reason for inability to determine healing will be recorded. Fisher's Exact Test will be used to assess possible significance of a difference in cuff closure scores between test and reference groups. Additionally, healing will be characterized using a predetermined list of binary assessment questions, these will not be statistically compared, but serve to characterize individual healing scores.

(3) Comparison of implant passing rates

The percentage of subjects experiencing implant (either clip or suture) passing by six-weeks and six-months post-operative will be compared between test and control groups using Fisher's Exact Test.

(4) Frequency of implant passing events associated with an Adverse Event

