9.4.3 ANALYSIS OF THE PRIMARY SAFETY ENDPOINT

The primary safety endpoint in this study is the rate of vaginal cuff dehiscence through six months. Vaginal cuff dehiscence is defined as rupture of the surgical wound requiring surgical re-intervention. Subjects who experience vaginal cuff dehiscence up to six months after surgery will also be considered a cuff closure failure.

The number and proportion of subjects with vaginal cuff dehiscence at 6 weeks will be presented. The 95% confidence interval of the proportion will also be reported.

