9.4.4 ANALYSIS OF SECONDARY EFFICACY ENDPOINTS

Secondary Endpoint (1) Cuff closure (compared between test and reference groups) will be assessed (yes or no) by an independent surgeon at one and six weeks, as well as at six months.

Data collection: Surgeon will visually assess vaginal cuff closure, indicating whether the vaginal mucosa is intact. If the vaginal cuff closure is determined not to be intact, then failure of this study endpoint will be indicated and the subject will be included in the ITT population for remaining study endpoints. If additional surgical intervention is necessary to address lack of cuff closure, follow-up will restart following the new procedure date. In this circumstance the new follow-up schedule will be included in the evaluation of remaining efficacy endpoints in the ITT population and will be included in the safety population.

Acceptance Criteria: Endpoint success at each timepoint is defined as test group cuff closure failure rate less than or equal to that of the reference group.

Statistical Analysis Method: A two-sided Fisher's Exact Test will compare (test versus reference) rate of dehiscence at each timepoint. Assessment of this endpoint is independent of primary study endpoint results.

Secondary Endpoint (2) Cuff healing (compared between test and reference groups), will be assessed (yes or no) by an independent surgeon at six weeks and six months.

Data collection: Surgeon visual assessment of cuff healing is limited to a single binary assessment ("healed" or "not healed"). Additional descriptive observations are included during data collection but are not used in comparative analysis. If the vaginal cuff is determined not to be healed, then failure of this study endpoint will be indicated. If additional surgical intervention is necessary, follow-up will restart following the new procedure date. In this circumstance the new follow-up schedule will be included in the evaluation of remaining efficacy endpoints in the ITT population and will be included in the safety population.

Acceptance Criteria: Endpoint success is defined as a test group cuff healing failure rate less than or equal to that of the reference group.

Statistical Analysis Method: A two-sided Fisher's Exact Test will compare (test versus reference) rate of visually assessed, failed cuff healing at each post-operative timepoint. Assessment of this endpoint is independent of the primary safety endpoint.

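### The stopping rule pauses on dehiscences but stops on closure failures, a term the protocol uses in two senses, and it divides test-device cases by all enrolled women; both need aligning (minor).

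*Combined protocol and SAP*

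**What the plan says.** Section 10.1.2 has two steps. The study pauses for unblinded review by the independent safety monitor when "at least three cuff dehiscences and a failure rate of at least 5% of the enrolled study population has been realized". After that review, "the study will continue unless vaginal cuff closure failures with study test device" (the Zip-stitch clips) "are found to be at least 3 cases and a rate of greater than 5% of the enrolled study population". The stop applies only to the test device.

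Section 3.1 fixes the first event: "Vaginal cuff dehiscence is defined as rupture of the surgical wound requiring surgical re-intervention". The second event is not defined in 10.1.2, and other sections use it in two ways.

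- **Wider than dehiscence.** Section 3.2 says of the visual closure endpoint that "subjects could fail this secondary endpoint without failing the primary study safety endpoint". Section 9.4.3 says "Subjects who experience vaginal cuff dehiscence up to six months after surgery will also be considered a cuff closure failure". Section 9.4.4 says "If the vaginal cuff closure is determined not to be intact, then failure of this study endpoint will be indicated", and treats further surgery as something that may or may not follow.
- **Same as dehiscence.** The Fisher test for the closure endpoint in 9.4.4 "will compare (test versus reference) rate of dehiscence at each timepoint". Section 7.1 offers failed closure and dehiscence as alternative names for one event, and section 4.2 uses failed closure to stand for the primary safety measure.

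Section 10.2 adds that small mucosal openings that resolve without intervention are not counted as failures. Section 9.2 plans 39 test and 20 reference women (59), with a maximum of 44 and 22 (66).

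**The concern.** A stopping rule should give one answer for one set of data. Here the event that opens the review and the event that decides it have different names, and the deciding name has two meanings in the same document. The monitor would have to choose between them after seeing unblinded data, which a pre-specified rule is meant to avoid. A wrong choice matters most during enrolment, when a stop would spare further women.

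The percentage clause has a related mismatch. The numerator is test-device cases, while the denominator reads as everyone enrolled. The pause also needs at least 5% while the stop needs more than 5%. If enrolment goes past its target, these details raise the number of test-device cases needed to stop.

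**Working it through.** **Enrolment.** 35/(1 − 0.10) = 38.9, so 39 test women. 39/2 = 19.5, so 20 reference women. The total is 59, as section 9.2 states, and the maximum is 44 + 22 = 66. The documents give no operating characteristics for the stopping rule.

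**Does the 5% clause bind?** Three cases as a share of all enrolled women:

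| Enrolled | 3/N | Pause (≥ 5%) | Stop (> 5%) |
|---|---|---|---|
| 30 | 10.0% | met | met |
| 59 | 5.08% | met | met |
| 60 | 5.00% | met | not met |
| 61 | 4.92% | not met | not met |
| 66 | 4.55% | not met | not met |

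Up to 59 women the clause never binds, so the stop turns only on whether the test-device count is 2 or 3. From 60 to 66 women a fourth test case is needed, although three cases are 3/40 = 7.5% to 3/44 = 6.8% of the test arm.

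**Can the two meanings give different decisions?** At 30 women (20 test, 10 reference), suppose 2 test dehiscences, 1 reference dehiscence and 1 test cuff not intact but managed without surgery.

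- Pause: 3 dehiscences, 3/30 = 10%. Met.
- Stop, counting dehiscences: 2 test cases. Continue.
- Stop, counting cuffs not intact: 3 test cases, 3/30 = 10%. Stop.

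At that moment 59 − 30 = 29 women, 39 − 20 = 19 of them test, would remain to be enrolled.

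**How often?** The conflict needs at least 3 dehiscences overall, at most 2 on test, and test dehiscences plus open test cuffs of at least 3. I used binomial counts with dehiscence rate d in both arms and open-cuff rate o among test women without dehiscence. The documents give no value for o, so I assumed 2% to 10%. The protocol cites dehiscence of up to 5%; 1% and 2% are assumed alternatives.

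| d | 20 + 10 women | 39 + 20 women |
|---|---|---|
| 1% | 0.05% to 0.2% | 0.6% to 1.4% |
| 2% | 0.3% to 1.1% | 2.9% to 6.8% |
| 5% | 2.5% to 8.5% | 10.7% to 24.9% |

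These figures are illustrative and assume that all outcomes among the women counted are known.

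**What does the denominator change?** At 44 test women and an assumed true dehiscence rate of 5%:

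- Stop at 3 cases: P(at least 3 of 44) = 0.38.
- Current rule, all cases counted after enrolment passes 59: P(at least 4 of 44) = 0.18.
- Current rule, cases counted as they occur (3 needed up to 59 women, 4 after): 0.32 with 39 test women among the first 59, 0.35 with 42, and 0.36 with 43.

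The last two are favourable arrangements of the section 6.3 blocks of three to six. With two sites, 17 full triplets plus two part-filled blocks with 4 leading test assignments each give 34 + 8 = 42. With three sites, 16 triplets plus 4 + 4 + 3 give 32 + 11 = 43.

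**The case against.** The strongest reply is that the intent is clear. Section 10.1.2 presents the rule as one of subject safety. Dehiscence is the primary safety endpoint, whereas visual closure is a secondary efficacy endpoint. The pause sentence already uses failure rate for dehiscence, and section 10.2 takes self-resolving openings out of the failures. This largely stands: dehiscence is the likelier meaning. It does not settle the matter, because 9.4.4 fails any cuff that is not intact, and 10.2 covers only small openings that resolve, not an open cuff that persists or is managed without surgery.

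Safeguards also exist. Under 10.1.5 one independent physician adjudicates all safety events and reviews any stoppage analysis, and 10.1.2 allows suspension for unacceptable risk. They limit the harm. Adjudication settles what happened to a woman, though, not which event the rule counts.

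On the denominator, the protocol does not say in so many words that the enrolled study population means both arms. It is the natural reading, since the same phrase serves the pause, which counts both arms.

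A reader might infer three stronger conclusions that the documents do not support:

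- **That the plan commits to stopping on every open cuff.** The context points the other way.
- **That conflicting decisions are likely, citing 10.7% to 24.9%.** This needs an assumed open-cuff rate, the upper reported dehiscence rate in both arms, and outcomes on all 59 women, when target enrolment is complete and a stop spares no one further enrolment. The earlier clinical study in section 2.2 reported closure and normal healing in all ten subjects.
- **That the denominator weakens the rule at the planned size.** Up to 59 women it has no effect.

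**Conclusion.** The point holds as a minor correction. The pause and the stop name different events, and the stop event has two meanings in the protocol, so the rule read literally can give opposite decisions on the same data. That requires a specific pattern, and under the stated assumptions it is uncommon while enrolment is still open: about 1% or less at 30 women if dehiscence is 1% to 2%.

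The denominator and the strict inequality matter only at 60 to 66 women, where three test cases no longer stop the study. This rests on reading the denominator as all enrolled women. The loss in stopping probability ranges from 0.38 − 0.18 = 0.20 down to about 0.38 − 0.36 = 0.02 at a true 5% rate, depending on when cases are counted. Confidence is high about the wording conflict and lower about its practical consequence.

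**What to change.** In 10.1.2:

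1. Write *vaginal cuff dehiscence as defined in section 3.1* in both the pause and the stop.
2. Base the stop on at least 3 Zip-stitch dehiscences and at least 5% of women treated with Zip-stitch.
3. Let the pause also be met whenever at least 3 dehiscences reach 5% of either the enrolled women or the Zip-stitch-treated women, so that the pause cannot block the stop.

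The cost is two sentences, agreed with the safety monitor. The dehiscence-based boundary at 39 test women stays at 3. At up to 44 test women three cases always exceed 5% of the arm (3/44 = 6.8%), so the three-case floor decides both steps.

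There are two downsides. Open cuffs without re-operation would not count toward the formal stop and would rely on the monitor and discretionary suspension. Above 59 women the rule becomes somewhat more sensitive. At 44 test women and a true 5% rate, the stop probability is 0.38 against 0.18 to 0.36 now. At 66 women and an assumed overall rate of 2%, the pause probability is 0.15 against 0.04 to 0.12 now.

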10.1.3 CONFIDENTIALITY AND PRIVACY

Subject confidentiality is strictly held in trust by the participating investigators, their staff, and the sponsor and their agents. The study protocol, documentation, data, and all other information generated will be held in strict confidence. No information concerning the study or study data will be released to any unauthorized third party without prior written approval of the sponsor.

The study monitor, other authorized representatives of the sponsor, or representatives of the IRB may inspect all documents and records required to be maintained by the investigator, including but not limited to, medical records (office, clinic, or hospital) and any pharmacy records for the subjects in this study. The clinical study site will permit access to such records.

The study subject's contact information will be securely stored at each clinical site for internal use during the study. At the end of the study, all records will continue to be kept in a secure location for as long a period as dictated by local IRB and institutional regulations.

10.1.5 SAFETY OVERSIGHT

[name]. is the medical monitor for this study. [name] is an independent physician not affiliated with this clinical trial in any other way. [name] will be contacted in the event of any serious or unexpected adverse events to determine whether the SAE or AE is test article related. He will also provide independent safety review of any analysis related to study stoppage (See section 10.1.2 for study stoppage rules), as well as independent adjudication of all study safety events.

10.1.6 CLINICAL MONITORING

Clinical site monitoring is to be performed in compliance with ZSX Medical's Clinical Monitoring Standard Operating Procedure. Clinical monitoring is performed to ensure that the rights and well-being of human subjects are protected, that the reported trial data are accurate, complete, and verifiable, and that the conduct of this trial is in compliance with the currently approved protocol/amendment(s), with GCP, and with all applicable regulatory requirement(s). The clinical trial monitor will also be responsible for assisting the study sponsor in any resolving data queries that may result from site reporting.

Clinical monitoring will be performed by one or more Clinical Research Associates for as long as patients are in trial schedule. This includes, but is not limited to, patient involvement from recruitment to completion of follow-up and extension period phone calls, as outlined follow-up schedule in Section 1.3.

Monitoring will involve site facilities review, study trainings and query resolution, regular review and maintenance of essential trial documents for completeness and correctness, confirmation of accurate reporting of participant informed consent, safety data and study endpoints, and maintenance of records of monitoring communication.

Visits will include Site Initiation, regular Interim Visits dependent on enrollment progress and study safety and conformance, and a Closeout Visit. For-cause visits may also take place as appropriate and can be mandated by the Sponsor, the study IRB, FDA, or can be requested by the site. Monitoring reports will be produced following each visit, and all monitoring communication will be maintained.

10.1.7 QUALITY ASSURANCE AND QUALITY CONTROL

Each clinical site will perform internal quality management of study conduct, data collection, documentation and completion. An individualized quality management plan will be developed to describe a site's quality management.

Quality control (QC) procedures will be implemented beginning with the data entry system and data QC checks that will be run on the database will be generated. Any missing data or data anomalies will be communicated to the site(s) for clarification/resolution.

Following written Standard Operating Procedures (SOPs), the monitors will verify that the clinical trial is conducted and data are generated and biological specimens are collected, documented (recorded), and reported in compliance with the protocol, International Conference on Harmonisation Good Clinical Practice (ICH GCP), and applicable regulatory requirements (e.g., Good Laboratory Practices (GLP), Good Manufacturing Practices (GMP)).

The investigational site will provide direct access to all trial related sites, source data/documents, and reports for the purpose of monitoring and auditing by the sponsor, and inspection by local and regulatory authorities.

